# 3.2.6 Study Drug Exposure and Compliance

Study drug exposure and compliance will be presented using the Safety/ITT population.

Exposure to study drug will be presented cumulatively.

The number of cycles of study drug received is defined as the total number of cycles where the patient has received at least 1 dose of study drug in each cycle, and excluding any cycle(s) where the patient has not been dosed. The study drug exposure is recorded for each cycle where the number of capsules dispensed and number of capsules returned will be entered; where the number of capsules returned is equal to the number of capsules dispensed, then this indicates that the patients were not dosed at this specific cycle.

Duration of study drug is defined as: (date of last dose – date of first dose) + 1. If the date of last dose is missing then this will be imputed as the date of the last study drug dispensed.

Dose intensity (%) is defined as the percentage of the study drug a patient has taken compared to the amount of study drug the patient was meant to take. This will be calculated as:

Total cumulative dose received (mg) / total cumulative dose planned (mg) \*100

Total cumulative dose received (mg) is defined as the sum of all dose (mg) as recorded from the study drug administration eCRF page using each entry (date of last dose –date of first dose) + 1 \* dose in mg. If the date of last dose is missing then this will be imputed with the date of the last study drug dispensed.

Similarly, the total cumulative dose planned (mg) is defined as the sum of all planned dose (mg) as recorded from the study drug administration eCRF page using each entry (date of last dose –date of first dose) + 1 \* 300 mg. If the date of last dose is missing then this will be imputed with the date of the last study drug dispensed.

Treatment compliance is defined as the percent of actual amount of drug taken relative to the planned amount. It is calculated according to the following formula for the entire study:

% compliance = (# of capsules dispensed - # of capsules returned)/{(# of days in the dosing interval)\*(# capsules per daily dose)}\*100

where the # of days in the dosing interval excludes any days that the patient was instructed to hold dosing due to an AE.

Treatment compliance will also be summarized categorically, considering cut-offs of 80% and 120% for compliance.

The number of cycles of study drug received, total duration of study drug (weeks), dose density (%), total cumulative dose received (mg) and treatment compliance (%) will be summarized using continuous statistics. Treatment compliance (%), the number of patients with at least 1 dose change/interruption during

the duration of the study, and the reasons for dose change/interruption will be summarized as categorical variables.

Study drug administration, drug accountability, exposure and compliance will be presented by patient listings.

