- Dispense derazantinib capsules and perform drug accountability of returned drug. Note: To avoid unnecessary waste of study drug, in cases where treatment was interrupted and/or dose was reduced, the patient can continue dosing from the previously dispensed bottle until the next drug dispensing visit where re-supply is needed to maintain the protocol dosing regimen.

\* Patients who develop ocular symptoms or changes in visual acuity while on the study should be referred to an ophthalmologist for a complete eye examination.

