#### 7.1.2 Drug accountability

When a drug shipment is received, the Investigator or designee will check the amount and condition of the drug, check for appropriate local language in the label, drug expiration date, and acknowledge receipt in the IRT system. A Packing Slip will be included with the shipment and must be completed upon receipt and returned as instructed on the form. In addition, the Investigator or designee shall contact the Sponsor as soon as possible if there is a problem with the shipment.

A Drug Accountability Log will be provided for derazantinib capsules. The log must be kept current and should contain the protocol number, the name and clinical site of the Investigator, dates and quantities of drug received, patient's identification number to whom derazantinib capsules were dispensed, the date and quantity dispensed, and balance remaining, if from individual patient drug units, as well as the lot number, dose, and the initials of the dispenser. Drug accountability is performed to the capsule level.

To avoid unnecessary waste of derazantinib capsules, in cases where treatment was interrupted and/or dose was reduced, the patient can continue dosing from the previously dispensed bottle until the next drug dispensing visit where re-supply is needed to maintain the protocol dosing regimen.

At the end of the study or as directed, all study drug, including unused, partially used, or empty containers, will be returned to the designee as instructed by the Sponsor. Derazantinib capsules will be returned only after the study monitor has completed a final inventory to verify the quantity to be returned. The return of derazantinib capsules must be documented and the documentation must be included in the shipment. Unused drug supplies may be destroyed by the Investigator when approved in writing by the Sponsor and the Sponsor has received copies of the site's drug handling and disposition Standard Operation Procedures (SOPs) or equivalent.

All derazantinib capsules inventory forms must be made available for inspection by a Sponsor authorized representative or designee and regulatory agency inspectors. The Investigator is responsible for the accountability of all used and unused study supplies at the site.

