# 1.1 STUDY DESIGN

This is a multi-center, open label, single arm, Phase 2 study evaluating derazantinib in adult patients with inoperable or advanced intrahepatic cholangiocarcinoma (iCCA) and *FGFR2* genetic aberrations (GAs).

- **Substudy 1** enrolls patients with *FGFR2* fusions.
- Substudy 2 enrolls patients with *FGFR2* mutations or amplifications

Substudy 1 was considered pivotal and will enroll approximately 100 patients to determine the objective response rate (ORR).

Substudy 2 will use a Simon's two-stage design, with approximately 15 modified intent-to-treat (mITT) - evaluable patients in Stage 1, and an additional 28 mITT-evaluable patients if the study proceeds to Stage 2.

Patient eligibility will be assessed in two steps: 1) Molecular pre-screening to confirm *FGFR2* GA status (*FGFR2* fusions, or *FGFR2* mutations/amplifications; see Table 1 and Table 2, and Appendix 8 from the protocol) using validated/approved genetic testing devices; and 2) clinical screening procedures to confirm study treatment eligibility is confirmed by the tumor's *FGFR2* GA status.

Molecular pre-screening for FGFR2 fusions in Substudy 1 may be based on local or central testing. If pre-screening is performed based on a local test, then a central confirmation by the FGFR2 break-apart fluorescence in situ hybridization (FISH) Probe Kit test is required for Substudy 1 (FGFR2 fusions). Molecular pre-screening for FGFR2 mutations/amplifications in Substudy 2 should be based on next-generation sequencing (NGS) testing performed or commissioned by the respective study site.

Patients may be prescreened for the tumor's *FGFR2* GA status (prior to initiation of or during ongoing systemic therapy). If the patient is still receiving prior systemic therapy, clinical screening procedures will be delayed until radiographically confirmed disease progression or intolerance to the ongoing systemic therapy is documented. After the study treatment eligibility is confirmed, patients will be enrolled and treated with continuous 300 mg once daily (QD) of derazantinib capsules. A treatment cycle is defined as 28 days. Patients will receive treatment with derazantinib capsules until death, radiographic disease progression, unacceptable toxicity, or until another of the specified criteria is met for stopping therapy.

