PFS will be calculated as the time from first dose of study drug until disease progression as assessed by BICR, or death from any cause, whichever occurs first. Patients who either have no baseline tumor evaluation or have no post-baseline tumor evaluation will be censored at date of first dose. Patients who discontinue treatment due to reasons other than disease progression by BICR or death will be censored in the PFS analyses as the date of their last tumor evaluation prior to EOT. Patients who progress or die after missing  $\geq 2$  consecutive scheduled tumor assessments will be censored at the date of the last tumor evaluation prior to progression or death. Any disease progression as assessed by BICR, or death occurring after end of treatment visit are not taken into account as a PFS event. For missing end of treatment visit date, a +7 day window compared to the maximum of last dose date, last on treatment visit date will be applied to create a tentative end of treatment visit date and a cut-off for death occurring after this date.

The rules for censoring PFS are summarized in the table below:

Situation	Date of progression or consoring	Outcome
No baseline tumor assessments	Date of first dose	Censored
No post-baseline tumor evaluation	Date of first dose	Censored
Documented radiological	Date of radiological assessment of measured	Progressed
progression	lesions up to EOT	
No radiological progression	Date of last radiological assessment of measured	Censored
	lesions up to EOT	
Treatment discontinuation for	Date of last radiological assessment of measured	Censored
reasons other than radiological	lesions up to EOT	
disease progression by BICR or		
death		
Death before first PD assessment	Date of death	Progressed
Death between adequate assessment	Date of death	Progressed
visits		
Death or radiological progression	Date of last radiological assessment of measured	Censored
after more than two missed tumor	lesions prior to progression or death	
assessment or after end of treatment		

Table 2: Censoring scheme for PFS

The hypothesis being tested is:

Null Hypothesis H0: PFS  $3 \le 0.45$  and Alternative Hypothesis HA: PFS 3 > 0.45

Where PFS 3 is the proportion of patients with a PFS > 3 months (i.e. > 91 days).

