#### 3.2.8.1 Adverse Events

AEs will be coded using the MedDRA and assigned the grades (severities) based on NCI CTCAE, Version 4.03. For AEs not listed in the NCI CTCAE version 4.03, a similar grading system should be used as follows:

- Grade 1: Mild AE
- Grade 2: Moderate AE
- Grade 3: Severe AE
- Grade 4: Life-threatening or disabling AE
- Grade 5: Death

A treatment-emergent adverse event (TEAE) is defined as an AE with start date on or after the date of first dose and up to 30 days after last dose of study treatment (or until the start of a new anticancer therapy, whichever occurs earlier).

An overall TEAE incidence summary table will be produced and will include the number and percentage of patients with any TEAE, with any TEAE assessed by the Investigator as related to drug (related/not related), and with any serious TEAEs, drug-related serious TEAEs, TEAEs leading to permanent study drug discontinuation, drug-related TEAEs leading to permanent study drug discontinuation, TEAEs leading to study drug dose reduction or interruption, TEAEs leading to study drug dose reduction or interruption, drug-related TEAEs leading to study drug dose reduction or interruption, drug-related TEAEs leading to study drug dose reduction or interruption, drug-related TEAEs leading to study drug dose reduction or interruption, drug-related TEAEs leading to study drug dose reduction or interruption TEAEs leading to death, drug-related TEAEs leading to death will be summarized. The number of events will also be displayed.

For all event types listed above in the overall AE incidence summary table, tabulations by SOC and PT will also be produced. These will be presented by SOC and PT, sorted by decreasing frequency. Furthermore, TEAE, and drug-related TEAEs will also be summarized by SOC, PT, and maximum CTCAE grade, and sorted by decreasing frequency. Patients with more than one AE within a particular SOC are counted only once for that SOC. Similarly, patients with more than one AE within a particular PT are counted only once for that PT. For summaries by maximum CTCAE grade, patients with multiple AEs within a particular SOC or PT will be counted under the category of their most severe AE within that SOC or PT. AEs with missing CTCAE grade will be included in the missing counts.

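### Imputing a missing last-dose date as the last dispensing date understates duration of study drug and cumulative dose by up to about one cycle per affected patient

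*SAP*

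**What the plan says.** SAP 3.2.6 gives the formula "Duration of study drug is defined as: (date of last dose – date of first dose) + 1" and adds "If the date of last dose is missing then this will be imputed as the date of the last study drug dispensed". For cumulative dose received and cumulative dose planned, both summed over entries on the study drug administration page, it repeats the rule: "If the date of last dose is missing then this will be imputed with the date of the last study drug dispensed".

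The meaning of a dispensing date comes from the visit schedule. SAP 1.1 states "A treatment cycle is defined as 28 days". Protocol 5.4.1 has drug dispensed on Cycle 1 Day 1, and Protocol 5.4.3 lists for Day 1 (± 3 days) of every later cycle: "Dispense derazantinib capsules and perform drug accountability of returned drug". After an interruption or reduction, the patient may go on using an earlier bottle (Protocol 5.4.3, 7.1.2 and 7.4).

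Better information is collected. Protocol 7.1.2 states "Drug accountability is performed to the capsule level", and SAP 3.2.6 itself uses capsules dispensed and returned per cycle, both to decide whether a cycle was dosed and to compute compliance.

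Two other definitions use the last-dose date. SAP 3.2.8.1 counts an event as treatment-emergent from first dose "and up to 30 days after last dose of study treatment" (or until new anticancer therapy). SAP 3.2.7.1 builds a tentative End of Treatment date for PFS when the visit date is missing: a 7-day "window compared to the maximum of last dose date, last on treatment visit date will be applied". Neither says what to do when the last-dose date is itself missing.

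**The concern.** A dispensing date marks the start of a supply. Using it as the last-dose date credits one day of the final supply however much of it was taken. This is the earliest last dose compatible with the patient having started that supply, so the error runs in one direction.

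At stake is the accuracy of the exposure tables, which give the context for the safety results: duration, cumulative dose and dose intensity. The rule can also make Section 3.2.6 disagree with itself, because capsule counts in the same section may show that far more drug was taken.

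**Working it through.** The SAP states no figure for the effect of this rule, so there is nothing to reproduce. What follows is date arithmetic on the SAP's own formulas.

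**Inputs.** Cycle of 28 days (SAP 1.1). Dispensing on Day 1 of each cycle (Protocol 5.4.1, 5.4.3). Dose of 300 mg as three 100 mg capsules (Protocol 7.1.4 and Table 4). The quantity dispensed per visit is not stated; I assume 84 capsules, that is 3 × 28.

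**Duration.** The dispensing day of cycle n is 28(n − 1) + 1. If the true last dose is on day k of cycle n, then:

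- true duration = 28(n − 1) + k
- imputed duration = 28(n − 1) + 1
- loss = k − 1 days

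The loss is 0 days at k = 1, 13 at k = 14 and 27 at k = 28. It is 30 if the patient doses until a next visit that falls 3 days late (k = 31), and can be larger when an earlier bottle is carried over. With a fully taken last cycle:

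| Cycles | True days | Imputed days | Understated by |
|---|---|---|---|
| 1 | 28 | 1 | 96% |
| 2 | 56 | 29 | 48% |
| 4 | 112 | 85 | 24% |
| 9 | 252 | 225 | 11% |

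**Cumulative dose.** At 300 mg daily the largest nominal loss is 27 × 300 = 8,100 mg. At four cycles, 112 × 300 = 33,600 mg becomes 85 × 300 = 25,500 mg.

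**Conflict with capsule counts.** With 84 capsules dispensed on Cycle 1 Day 1 and none returned, the count gives 84 × 100 = 8,400 mg over 28 days. The imputation gives (1 − 1) + 1 = 1 day and 300 mg.

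**Dose intensity.** At a constant 300 mg the numerator and denominator shrink together and the ratio stays at 100%. After a reduction they do not. Take 300 mg for two cycles, then 200 mg from C3D1, over four full cycles:

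- true: (56 × 300 + 56 × 200) / (112 × 300) = 28,000 / 33,600 = 83.3%
- imputed: (56 × 300 + 29 × 200) / (85 × 300) = 22,600 / 25,500 = 88.6%

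The days removed are all at the reduced dose, so part of the reduction disappears.

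**Negative entries.** The rule is applied to each entry. If a reduction opens a new entry on day 94 after the last dispensing on day 85, and that entry has no last-dose date, its length is (85 − 94) + 1 = −8 days.

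**The case against.** The strongest defence is that the dispensing date is a documented contact with the drug and therefore a conservative lower bound. Assuming that the whole supply was taken would err the other way. That stands, and the fix should not assume full consumption when returns are unknown. It does not justify ignoring returns that were recorded, and it cannot explain a negative duration.

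It is also true that the number of cycles received (SAP 3.2.6) and treatment phase duration (SAP 3.2.1) do not use this rule, that accountability data are listed, and that 27 days is close to the worst case, not typical.

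Three stronger readings are tempting, and the documents do not support them.

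- **PFS.** A reader might infer that the cut-off falls to dispensing plus 7 days, so that later deaths drop out. The fallback in SAP 3.2.7.1 takes the later of last dose and last on-treatment visit. Dispensing takes place at a visit, so the imputed date can never be the later of the two by itself, and the imputation shortens the cut-off by 0 days. A patient dispensed drug only on C1D1 but seen on Day 15 has a cut-off of Day 22. Overall survival counts every death regardless.
- **TEAE window.** If the imputed date were reused, the window would close 30 − (k − 1) days after the true last dose: 17 days at k = 14 and 3 days at k = 28. But the rule is written only for exposure, and SAP 3.1.4 leaves missing values alone unless a rule is given. What remains is a gap: SAP 3.2.8.1 has no rule for a missing last-dose date.
- **Who is affected.** A reader might suppose that these are mainly early failures lost or dying at home, which would make censoring informative. The documents give neither the number nor the profile of such patients.

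**Conclusion.** The point holds for descriptive exposure. For each patient with a missing last-dose date, duration of study drug is understated by k − 1 days, nominally 0 to 27, with a matching loss of up to 8,100 mg at 300 mg daily. The proportional error is greatest in patients with few cycles. Dose intensity is unchanged at constant dose but can be overstated after a reduction, and an open entry that starts after the last dispensing gets a negative length.

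This rests on dispensing at each Day 1 visit and, for the capsule example, on an assumed 84-capsule supply. The trial-level effect cannot be given without the count of missing dates. The Substudy 1 ORR test is untouched, and the imputation does not move the PFS cut-off used for PFS 3. This is a minor correction, worth making because the rule is wrong in a known direction and better data are already collected.

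**What to change.** Replace the rule in SAP 3.2.6, for duration and for both cumulative doses, as follows.

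- **Returns known:** last dose = last dispensing date + (capsules dispensed − capsules returned) / capsules per dosing day − 1, allowing for documented holds, any every-other-day dosing and carried-over bottles. With 84 dispensed and 0 returned at 3 per day this gives day 28 of the cycle; with 42 returned it gives day 14.
- **Bounds:** no earlier than the entry's start date or the last date with documented dosing; no later than the End of Treatment visit, the discontinuation decision, death or data cut-off.
- **Returns unknown:** use the last date with documented dosing, and show the range from the dispensing date to the full supply capped as above.

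Report how many patients needed imputation. State in SAP 3.2.8.1 and 3.2.7.1 whether this date also governs the TEAE window and the tentative End of Treatment date. If it does govern the latter, the PFS cut-off could move later for some patients, so that choice should be fixed before the final analysis.

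The cost is a short SAP edit and slightly more programming, with no new data collection. Some uncertainty remains when returns are unknown.

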# 3.2.7 Analyses of Efficacy Variables

All efficacy data will be summarized by substudy as detailed below, and listed.

For Substudy 1, the Safety/ITT population will be used to analyze the efficacy data, with the mITT and PP population used for sensitivity analyses. For Substudy 2, the mITT population will be used to analyze the efficacy data, with the ITT and PP population used for the sensitivity analyses.

Assessments by Blinded Independent Central Review (BICR) consider two readers. Should there be disagreement between these two readers, an adjudicator decides which reader is correct. As such, all analyses which consider BICR assessments will be based upon the first reader by default, unless the second reader is selected following adjudication. BICR and local assessment will be analyzed and listed.

Waterfall plots, spider plots and swimmer plots will be produced to accompany efficacy analyses.

# 3.2.7.1 Analysis of Primary Efficacy Variable

#### **Substudy 1**

The primary efficacy endpoint for Substudy 1 will be ORR, defined as the achievement of confirmed CR or PR using RECIST v1.1(Eisenhauer 2009) as assessed by BICR.

Per protocol inclusion criteria, only patients with measurable disease by RECIST version 1.1 criteria should be enrolled. If a patient without measurable disease is enrolled, the ITT principle requires including these patients in the analyses. Hence, analyses will be based on patients with either measurable or non-measurable disease. For this purpose, non-CR/non-PD in patients with non-measurable disease will be considered equivalent to SD in patients with measurable disease, and the same rules will be applied.

Classification of best confirmed response is done according to the following hierarchy and rules:

- 1. CR: requires two consecutive CR response assessments a minimum of four weeks apart
- 2. PR: requires two consecutive PR response assessments OR a PR response followed by a consecutive CR response assessment (a minimum of four weeks apart)
- 3. SD: requires only one SD response assessment (provided minimum criteria for SD duration met)
- 4. Non-CR/Non-PD (non-measurable disease patients only): requires only one Non-CR/Non-PD response assessment (provided minimum criteria for Non-CR/Non-PD duration met)
- 5. PD: requires only one PD response assessment

The minimum duration for SD and Non-CR/Non-PD is defined as at least 6 weeks i.e. 42 days, where the duration is calculated from the start of treatment until the criteria of SD is met.

The classification as per RECIST 1.1 (Eisenhauer 2009) is summarized in Table 1 below.

Table 1	: Best	overall	response	when	confirmation	of	CR	and	PR	required
I GOIC I			response		communication	•••	~			i cquii cu

Overall response						
First time point	Subsequent time point	BEST overall response				
CR	CR	CR				
CR	PR	SD, PD or PR*				
CR	SD	SD provided minimum criteria for SD duration met, otherwise PD				
CR	PD	SD provided minimum criteria for SD duration met, otherwise PD				
CR	NE	SD provided minimum criteria for SD duration met, otherwise NE				
PR	CR	PR				
PR	PR	PR				
PR	SD	SD				
PR	PD	SD provided minimum criteria for SD duration met, otherwise PD				
PR	NE	SD provided minimum criteria for SD duration met, otherwise NE				
NE	NE	NE				

CR = complete response, PR = partial response, SD = stable disease, PD = progressive disease, and NE = inevaluable.

\* If a CR is truly met at first time point, then any disease seen at a subsequent time point, even disease meeting PR criteria relative to baseline, makes the disease PD at that point (since disease must have reappeared after CR). Best response would depend on whether minimum duration for SD was met. However, sometimes 'CR' may be claimed when subsequent scans suggest small lesions were likely still present and in fact the patient had PR, not CR at the first time point. Under these circumstances, the original CR should be changed to PR and the best response is PR.

For patients with non-measurable disease, SD should be replaced by non-CR/Non-PD

If the best overall response has any special cases or difficulty from unexpected data, then these may be checked and discussed with the study team to decide which best overall response is best suited.

As specified in RECIST 1.1, repeated 'NE' time point assessments complicate best response determination. Should a CR/PR be followed by one or more NE response and then a CR/PR, then confirmed response would be achieved (as an example PR-NE-PR will be considered as a confirmed response).

Patients without efficacy assessments are considered non-responders, and included in the analysis.

Hypothesis testing (null hypothesis  $[H_0]$  versus alternative hypothesis  $[H_A]$ ) were performed at the interim and will be performed in the final analyses as specified below:

Null Hypothesis H0: ORR  $\leq 0.10$  and Alternative Hypothesis HA: ORR > 0.10

The hypothesis testing will be performed using exact test for binomial proportion at a one-sided 2.5% significance level. Point estimates and exact 2-sided 95% confidence intervals (Clopper-Pearson) will be provided. If the p-value is  $\leq$  to 2.5% (one-sided), or equivalently the lower limit of the confidence interval is > 10%, the null hypothesis will be rejected.

Considering the number of patients per site planned in this study, the site effect and treatment by site interaction will not be evaluated.

#### Substudy 2

The primary efficacy endpoint for Substudy 2 will be the proportion of patients who have PFS at 3 months from the first date of receiving study drug as assessed by survival status or central radiology review RECIST 1.1.

PFS will be calculated as the time from first dose of study drug until disease progression as assessed by BICR, or death from any cause, whichever occurs first. Patients who either have no baseline tumor evaluation or have no post-baseline tumor evaluation will be censored at date of first dose. Patients who discontinue treatment due to reasons other than disease progression by BICR or death will be censored in the PFS analyses as the date of their last tumor evaluation prior to EOT. Patients who progress or die after missing  $\geq 2$  consecutive scheduled tumor assessments will be censored at the date of the last tumor evaluation prior to progression or death. Any disease progression as assessed by BICR, or death occurring after end of treatment visit are not taken into account as a PFS event. For missing end of treatment visit date, a +7 day window compared to the maximum of last dose date, last on treatment visit date will be applied to create a tentative end of treatment visit date and a cut-off for death occurring after this date.

The rules for censoring PFS are summarized in the table below:

Situation	Date of progression or consoring	Outcome
No baseline tumor assessments	Date of first dose	Censored
No post-baseline tumor evaluation	Date of first dose	Censored
Documented radiological	Date of radiological assessment of measured	Progressed
progression	lesions up to EOT	
No radiological progression	Date of last radiological assessment of measured	Censored
	lesions up to EOT	
Treatment discontinuation for	Date of last radiological assessment of measured	Censored
reasons other than radiological	lesions up to EOT	
disease progression by BICR or		
death		
Death before first PD assessment	Date of death	Progressed
Death between adequate assessment	Date of death	Progressed
visits		
Death or radiological progression	Date of last radiological assessment of measured	Censored
after more than two missed tumor	lesions prior to progression or death	
assessment or after end of treatment		

Table 2: Censoring scheme for PFS

The hypothesis being tested is:

Null Hypothesis H0: PFS  $3 \le 0.45$  and Alternative Hypothesis HA: PFS 3 > 0.45

Where PFS 3 is the proportion of patients with a PFS > 3 months (i.e. > 91 days).

A Simon's two-stage design will be used, with approximately 15 patients in Stage 1, and an additional 28 patients if the study proceeds to Stage 2.  $H_0$  will be rejected if a PFS 3 is observed in 25 or more of these 43 patients. The type I error rate is 0.0481, and power is approximately 0.8 when the true PFS 3 rate for derazantinib is p1 = 0.65.

Point estimates, exact 2-sided 95% confidence intervals (Clopper-Pearson) and associated p-value will be provided.

PFS will be analyzed using Kaplan-Meier methodology (Kaplan & Meier 1958). The median duration of PFS will be presented along with the standard error and 2-sided 95% CI. If they are calculable, the 25th and 75th percentiles and the 2-sided 95% CIs around the percentiles will be presented. Kaplan-Meier estimates at 3, 6, 9 and 12 months will also be presented. The Kaplan-Meier survival curves will also be presented.

Additional PFS sensitivity analyses which consider alternative censoring methods as outlined in FDA guidelines (FDA 2018, FDA 2015) will be conducted in the same manner, as described above. These will be performed for the Safety/ITT and mITT populations:

- Sensitivity analysis 1 in Table 3 uses a conservative approach by assigning the date of discontinuation, or missed tumor assessment followed by PD or death as an event date.
- Sensitivity analysis 2 in Table 4 includes clinical progression as an event.
- Sensitivity analysis 3 in Table 5 evaluates PFS including post EOT radiological assessments.

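### The PFS text and its summary table set different missed-scan thresholds, so one patient can pass or fail PFS 3; unscanned on-treatment deaths also have no stated precedence

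*SAP*

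**What the plan says.** SAP 3.2.7.1, under Substudy 2, defines PFS from first dose to "disease progression as assessed by BICR, or death from any cause, whichever occurs first". The running text then gives the rules that matter here:

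- **Missed scans.** Patients who progress or die after missing two or more (printed as ≥ 2) "consecutive scheduled tumor assessments will be censored at the date of the last tumor evaluation prior to progression or death".
- **No scan.** "Patients who either have no baseline tumor evaluation or have no post-baseline tumor evaluation will be censored at date of first dose".
- **Cut-off.** "Any disease progression as assessed by BICR, or death occurring after end of treatment visit are not taken into account as a PFS event".

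It continues "The rules for censoring PFS are summarized in the table below", which introduces Table 2. The missed-assessment row of Table 2 applies "after more than two missed tumor" assessments, with no requirement that they be consecutive. Table 2 also has two rows that censor at first dose, "No baseline tumor assessments" and its counterpart for no post-baseline evaluation. A further row, "Death before first PD assessment", makes death an event on its own date.

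Tables 3 to 5 (the sensitivity schemes) and Table 8 (TTP on derazantinib) also use more than two. Table 3 uses that trigger to assign an event at the first missed assessment rather than to censor. PFS 3 is the proportion of patients with PFS beyond 91 days, and H0 is rejected with 25 or more successes in 43. SAP section 4 does not mention either point.

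**The concern.** There are two separate problems.

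**Threshold.** A summary table cannot carry a different trigger from the text it summarizes. The two rules part at exactly two missed scans: the text censors, while Table 2's missed-scan row does not apply and its row for documented radiological progression makes the PD an event.

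**Precedence.** A patient who dies on treatment before any post-baseline scan meets both the first-dose censoring rule and the rule making death an event. This overlap lies inside the text and inside each of Tables 2 to 5, not between them. The no-baseline rule overlaps with on-treatment death in the same way. Such patients are foreseen, because SAP 2.2 keeps patients who die during the treatment period in the mITT population.

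This derivation produces the Substudy 2 primary endpoint, the secondary PFS of both substudies (SAP 3.2.7.2.1) and investigator-assessed PFS (SAP 3.2.7.3.3). Two programmers following the SAP could reach different primary counts. In an open-label single-arm study, settling the rule after results are known would be hard to defend.

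**Working it through.** **1. The plan's own figures.** With 15 patients in Stage 1, stopping at 7 or fewer, and rejection at 25 or more of 43:

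P(reject) = Σ (x = 8 to 15) P(X₁ = x; 15, p) × P(X₂ ≥ 25 − x; 28, p)

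This gives 0.0481 at p = 0.45 and 0.8035 at p = 0.65, matching the stated 0.0481 and approximately 0.8. A boundary of 24 would give a type I error of 0.0798, so a single success matters.

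**2. Scan days.** Protocol 6.9 schedules scans at C3D1, C5D1 and C7D1, then every three cycles. With 28-day cycles, day 1 of cycle c is study day 28(c − 1) + 1. The scans fall on days 57, 113, 169, 253, 337 and 421.

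**3. Exactly two missed scans, then on-treatment PD at the next scheduled scan.**

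| Last evaluation | Missed | PD | Gap | Text | PFS > 91? | Table 2 | PFS > 91? |
|---|---|---|---|---|---|---|---|
| Baseline / day 1 | 57, 113 | 169 | 24 weeks | censored no later than first dose | no | event day 169 | yes |
| Day 57 | 113, 169 | 253 | 28 weeks | censored day 57 | no | event day 253 | yes |
| Day 113 | 169, 253 | 337 | 32 weeks | censored day 113 | yes | event day 337 | yes |
| Day 169 | 253, 337 | 421 | 36 weeks | censored day 169 | yes | event day 421 | yes |

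A confirmation scan 4 to 5 weeks after a day-57 response falls on days 57 + 28 = 85 to 57 + 35 = 92. A last evaluation on days 85 to 91 therefore behaves like the second row.

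**4. Effect on the decision.** Take 24 other successes plus one patient from the first two rows. Table 2 gives 25/43, which rejects. The text gives 24/43, which does not. If the censored patient were left out instead of counted as a failure, the text gives 24/42, still 24 successes.

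**5. Illustration with assumed counts.** The documents give no number of affected patients. Suppose the true rate under Table 2 is 0.65 and k of 43 patients become failures under the text, so p = 0.65 − k/43. Power is then 0.7148, 0.6097 or 0.4954 for k = 1, 2 or 3. Conversely, if the rate under the text is 0.45 and Table 2 gives 0.45 + k/43, the rejection probability is 0.0864, 0.1432 or 0.2203.

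**6. Unscanned on-treatment deaths.** Suppose 24 of 43 patients are beyond day 91, the other 19 are failures by day 91 of which k are unscanned deaths, and there is no other censoring by day 91.

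- Deaths as events: 24/43 = 0.558.
- Deaths censored at first dose: 24/(43 − k) = 24/42 = 0.571, 24/40 = 0.600 and 24/37 = 0.649 for k = 1, 3 and 6.

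The inflation factor is n/(n − k): 1.024, 1.075 and 1.162 for n = 43, and 1.010, 1.031 and 1.064 for n = 100 (Substudy 1). The PFS 3 count stays at 24, because a death by day 91 fails PFS 3 on either reading. Only an unscanned death after day 91 would change it.

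**The case against.** **The threshold conflict turns on one printed sign.** Five tables say more than two in words. The SAP is not consistent with its inequality signs elsewhere: the Substudy 1 alternative is printed with ≥ in section 1.4 and > in section 3.2.7.1. The sign is worth confirming. Nothing shows that it is wrong, and even with > the text would require consecutive scheduled assessments where the table does not.

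**The cases are narrow.** This stands. The threshold reaches PFS 3 only if a patient misses exactly two consecutive scans, was last evaluated by day 91, stays on treatment, and then has central PD before the end-of-treatment cut-off. No document says that such a patient exists, and 24 versus 25 is a chosen boundary case rather than an estimate.

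**The specific death row should override the general no-scan row.** That is the more coherent reading, but the SAP does not say so.

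**The same death row may cover a death after exactly two missed scans.** It may. Table 2 is unclear there, so deaths are not used in the threshold counts. On that reading the conflict would extend to deaths rather than shrink.

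**The Kaplan-Meier figures assume no other censoring by day 91.** Correct. They show direction and scale only.

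**Aligning the sentence to the tables would be equally valid.** Either threshold removes the contradiction. The text's version is the natural choice because Table 2 is described as its summary. Following the text does mean that an unscanned death after two missed scans is censored at first dose. That is a consequence of the SAP's existing missed-scan rule.

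**Conclusion.** The concern holds. The derivation behind the Substudy 2 primary endpoint states two incompatible missed-scan rules. For a patient last evaluated by day 91 who misses exactly two consecutive scans and then has on-treatment PD, they give opposite PFS 3 results. One such patient can decide between 24 and 25 successes. This assumes that a patient censored by day 91 does not meet PFS 3. That is the literal reading of PFS beyond 91 days and fits the full-population denominator in SAP 3.1.1, but the SAP does not say it.

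The missing precedence for unscanned on-treatment deaths is a separate ambiguity. It mainly affects Kaplan-Meier PFS, biasing it upward if early deaths are censored at first dose. The size depends on the number of such deaths, which the documents do not give.

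The Simon design figures and the Substudy 1 primary endpoint (ORR) are unaffected. Because the cases are uncommon, this should be corrected, but it does not undermine the design.

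**What to change.** Before database lock, amend the SAP wording as follows:

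1. Use one missed-assessment threshold, including the word consecutive, in both the text and Table 2. Two or more consecutive is the natural choice. Carry it to Tables 3 to 5 and Table 8, or state that they differ on purpose. Table 3 keeps its event at the first missed assessment.
2. State the order of precedence. First, PD or death after the end-of-treatment cut-off is not an event, where the table applies that cut-off. Second, the missed-assessment rule applies, censoring at the last evaluation, or at first dose if there is no post-baseline evaluation. Otherwise, an on-treatment death before any post-baseline scan is an event on the date of death.
3. Keep first-dose censoring for patients with no baseline evaluation, stating whether an on-treatment death overrides it. Keep it also for patients with no post-baseline evaluation and no qualifying death.
4. State that a patient censored on or before day 91 counts as not meeting PFS 3.

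The cost is SAP wording only. Sample size, decision boundary and data collection do not change.
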